- 3. Physical Examination must include height and weight. The patient's weight in kilograms must be determined before the start of each cycle.
- 4. Vital signs include: pulse, blood pressure, temperature, respiratory rate, and oxygen saturation.
- 5. **Hematology** must include CBC with differentials. Screening CBC done within 14 days of start of treatment. Must be repeated within 3 days of C1D1.
- 6. **Chemistry** must include comprehensive metabolic panel (albumin, alkaline phosphatase, total bilirubin, bicarbonate, BUN, calcium, chloride, creatinine, glucose, potassium, total protein, SGOT [AST], SGPT [ALT], sodium) magnesium, phosphorus amylase, lipase, thyroid function tests (fT4, and TSH) and LDH. Screening comp done within 14 days of start of treatment. Must be repeated within 3 days of C1D1. Screening magnesium, phosphorus, amylase, lipase, thyroid function tests (fT4 and TSH) and LDH must be done within 7 days of starting treatment.
- 7. **HIV, Hep B and Hep C tests** include: HIV I/II antibodies, Hepatitis B surface antigen, core antibody and Hepatitis C antibody. Must be done within 6 months of initiating treatment.
- 8. **Pregnancy test** includes: serum β-HCG or urine pregnancy test for women of child-bearing potential. If the urine test is positive or cannot be confirmed as negative, a serum pregnancy test will be required. Screening pregnancy tests must be performed within 7 days of starting treatment.
- 9. **EBV PCR:** screening EBV PCR must be done within 7 days of starting treatment. It is done on Cycle 2 Day 1, Cycle 4 Day 1, then odd cycles only starting in Cycle 5.
- 10. **Baseline FDG-PET/CT** simulation will be done following an initial consultation in Radiation Oncology and prior to starting therapy. Only required for patients who will be receiving radiation therapy.
- 11. **Pulmonary Function tests** include: DLCO at minimum.
- 12. **Baseline tumor biopsy:** all study participants will be required to have a biopsy that confirms extranodal NK/T cell lymphoma. If a biopsy is already done, 20 unstained slides from archived tissue will be requested for correlative studies if possible. The biopsy must be done prior to initiation of treatment.
- 13. **Research biopsies:** on-treatment biopsies are mandatory for all study participants. Biopsies will be done Cycle 1 (between days 8-20), and Cycle 4 (between days 8-20), except in cases where due to the location of disease, biopsy would be associated with unnecessary risk to the patient.

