- 14. Tumor Assessment: is the response assessment after PET scans. Refer to Section 12.0 Criteria for Therapeutic Response/Outcome Assessment.
- 15. **Pembrolizumab**: Pembrolizumab is administered every 3 weeks (21 days) on Day 1 of each cycle, ± 3 days. Pembrolizumab is given 200m via IVPB infusion over 30 minutes (+/- 5 minutes).
- 16. **Reassessment by PET after 2 Cycles of pembrolizumab:** If there is no evidence of disease progression, participant will receive another 2 cycles of pembro. If evidence of disease progression on PET but with clinical improvement, participant can be considered for another 2 cycles of pembro after discussion with the study PI. Patients with progression of disease without evidence of clinical improvement will proceed to 2 cycles of SMILE chemotherapy and ISRT.
- 17. **Reassessment by PET after 4 Cycles of pembrolizumab**: If Complete Response (CR) by PET, patients will begin 45 Gy of involved site radiation (ISRT), and an additional 6 months (8 cycles) of maintenance pembrolizumab. ISRT will begin 2-6 weeks after Cycle 4 of pembrolizumab. Patients with less than CR will undergo a biopsy. If biopsy shows no evidence of lymphoma, patients will proceed with same treatment as those with PET CR. Patients with less than CR by PET and persistent evidence of disease on biopsy after 4 cycles of pembro will proceed to 2 cycles of SMILE chemotherapy and ISRT.
- 18. **Follow-up** includes: standard clinic visit and laboratory tests (CBC, comp only). EBV PCR every 3 months for 3 years. Imaging to be obtained every 6 months for 2 years post treatment. cfDNA to be collected 6 months, 1 year, and 2 years into follow up or until a new therapy is initiated.
- 19. PET/CT to be completed at baseline only if the patient will not be receiving radiation therapy.
- 20. Patients will be followed by PET/CT (skull apex to midthigh). If PET/CT is not feasible, patients may be followed with CT CAP plus CT nasal cavity (for patients with nasal cavity disease) after discussion with MSK PI. If followed by PET/CT, additional diagnostic CT is NOT required.
- 21. cfDNA to be collected at C1D1, C4D1, after SMILE or at C5D1 of pembrolizumab, end of treatment, and 6 months, 1 year, and 2 years into follow up or until a new therapy is initiated.

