- 5. **Hematology** must include CBC with differential. Screening CBC done within 14 days of start of treatment. Must be repeated within 3 days of C1D1.
- 6. **Chemistry** must include comprehensive metabolic panel (albumin, alkaline phosphatase, total bilirubin, bicarbonate, BUN, calcium, chloride, creatinine, glucose, potassium, total protein, SGOT [AST], SGPT [ALT], sodium, magnesium, phosphorus), amylase, lipase, and thyroid function tests (fT4, and TSH) and LDH. Screening comp done within 14 days of start of treatment. Must be repeated within 3 days of C1D1. Screening amylase, lipase, thyroid function tests (fT4 and TSH) and LDH must be done within 7 days of start of treatment.
- 7. **HIV, Hep B and Hep C tests** include: HIV I/II antibodies, Hepatitis B surface antigen, core antibody and Hepatitis C antibody. Must be done within 6 months of initiating treatment.
- 8. **Pregnancy test** includes: serum β-HCG or urine pregnancy test for women of child-bearing potential. If the urine test is positive or cannot be confirmed as negative, a serum pregnancy test will be required. Screening pregnancy tests must be performed within 7 days of starting treatment.
- 9. **EBV PCR:** screening EBV PCR must be done within 7 days of start of treatment. It is done on Cycle 2 Day 1, Cycle 4 Day 1, then odd cycles only starting in Cycle 5.
- 10. **Baseline FDG-PET/CT** simulation will be done following an initial consultation in Radiation Oncology and prior to starting therapy. Only required for patients who will be receiving radiation therapy.
- 11. **Pulmonary Function tests** include: DLCO at minimum
- 12. **Baseline tumor biopsy:** all study participants will be required to have a biopsy that confirms extranodal NK/T cell lymphoma. If a biopsy is already done, 20 unstained slides from archived tissue will be requested for correlative studies if possible. The biopsy must be done prior to initiation of treatment.
- 13. **Research biopsies:** on-treatment biopsies are mandatory for all study participants. Biopsies will be done Cycle 1 (between days 8-20), and Cycle 4 (between days 8-20), except in cases where due to the location of disease, biopsy would be associated with unnecessary risk to the patient.
- 14. **Tumor Assessment:** is the response assessment after PET scans. Refer to Section 12.0 Criteria for Therapeutic Response/Outcome Assessment.

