# 11.3 Adverse Events Reporting Procedures

All AEs (e.g., any new event or worsening in severity or frequency of a pre-existing condition or laboratory finding) with an onset date after the subject signs consent for study participation must be promptly documented on the appropriate summary. Details of the event must include severity, relationship to study drug, duration, action taken, and outcome.

All AEs that are considered related to study procedures must be followed to resolution or stabilization if improvement is not expected.

AEs should be reported from the time the subject signs consent through 30 days post-last study intervention. In addition, the Investigator should report any AE that may occur after this time period that is believed to have a reasonable possibility of being associated with study intervention. If a subject discontinues study prior to receiving any study intervention, AEs must be reported through the end-of-study visit. AEs which completely resolve and then recur should be recorded as a new AE. For subjects who complete the end of study visit less than 30 days following the last study intervention, a follow up of ongoing AEs should be attempted by telephone and documented in the subject's source. AEs continuing at 30 days post-last treatment should have a comment in the source by the Investigator that the event has stabilized or is not expected to improve.

The Principal Investigator is responsible for evaluating all AEs, obtaining supporting documents, and determining that documentation of the event is adequate. Adverse events will be assigned a severity grade using the NCI CTCAE grading scale v4.0 and recorded. Furthermore, the occurrence of grade 2 or higher immune-related adverse events will be collected and designated as immune-related events of clinical interest (irAEs).

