# 11.5 Dose Modification and toxicity management for immune-related AEs associated with pembrolizumab

AEs associated with pembrolizumab exposure may represent an immunologic etiology. These immune-related AEs (irAEs) may occur shortly after the first dose or several months after the last dose of pembrolizumab treatment and may affect more than on body system simultaneously. Therefore, early recognition and initiation of treatment is critical to reduce

complications. Based on existing clinical study data, most irAEs were reversible and could be managed with interruptions of pembrolizumab, administration of corticosteroids and/or other supportive care. For suspected irAEs, ensure adequate evaluation to confirm etiology or exclude other causes. Additional procedures or tests such as bronchoscopy, endoscopy, skin biopsy may be included as part of the evaluation. Based on the severity of irAEs, withhold or permanently discontinue pembrolizumab and administer corticosteroids. Dose modification and toxicity management guidelines for irAEs associated with pembrolizumab are provided in Table 6.

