AST / ALT elevation or Increased bilirubin	Grade 2 ª	Withhold	Administer     corticosteroids     (initial dose of         0.5- 1 mg/kg     prednisone or     equivalent)     followed by     taper	Monitor with liver function tests (consider weekly or more frequently until liver enzyme value returned to baseline or is stable
	Grade 3 b or 4 c	Permanently discontinue	Administer     corticosteroids     (initial dose of 1-     2 mg/kg     prednisone or     equivalent)     followed by     taper	
Type 1 diabetes mellitus (T1DM) or Hyperglycemia	Newly onset T1DM or Grade 3 or 4 hyperglycemia associated with evidence of β-cell failure	Withhold d	Initiate insulin replacement therapy for participants with T1DM     Administer antihyperglycemic in participants with hyperglycemia	Monitor participants for hyperglycemia or other signs and symptoms of diabetes.
Hypophysitis	Grade 2 Grade 3 or 4	Withhold	Administer corticosteroids and initiate	Monitor for signs and symptoms of hypophysitis
	Grade 3 or 4	Withhold or permanently discontinue d	hormonal replacements as clinically indicated.	(including hypopituitarism and adrenal insufficiency)
Hyperthyroidism	Grade 2	Continue	Treat with non- selective beta- blockers (e.g.,	Monitor for signs and symptoms of thyroid disorders.
TT 4 19	Grade 3 or 4	Withhold or permanently discontinue d	propranolol) or thionamides as appropriate	
Hypothyroidism	Grade 2, 3, or 4	Continue	Initiate thyroid     replacement     hormones (e.g.,     levothyroxine or     liothyroinine)	Monitor for signs and symptoms of thyroid disorders.

			per standard of care
Nephritis grading according to increased creatinine or acute kidney injury	Grade 2 Grade 3 or 4	Withhold  Permanently discontinue	Administer corticosteroids (prednisone 1 to 2 mg/kg or equivalent) followed by taper.      Monitor changes of renal function      renal function
Neurological Toxicities	Grade 2 Grade 3 or 4	Withold  Permanently Discontinue	Based on severity of AE, administer corticosteroids      Based on evaluation to confirm etiology and/or exclude other causes
Myocarditis	Grade 1 Grade2, 3 or 4	Withhold  Permanently discontinue	Based on severity of AE administer corticosteroids      Based on evaluation to confirm etiology and/or exclude other causes

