#### Likely:

Decrease in function of the thyroid gland (if thyroid is in the ISRT field) Transient odynophagia

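### No TSH or fT4 is scheduled after End of Treatment, although the protocol warns of late immune-related events and of thyroid decline after in-field radiation

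*Combined protocol and SAP*

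**What the plan says.** The Follow-up column of each calendar carries its own footnote: 18 for stage I/II (section 10.1) and 17 for stage III/IV (section 10.2). Both define the visit as "standard clinic visit and laboratory tests (CBC, comp only", with EBV PCR, imaging and cell-free DNA on their own timetables.

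Footnote 6 defines the Chemistry row. In 10.1 it adds "thyroid function tests (fT4, and TSH) and LDH" after the bracketed metabolic panel. In 10.2 the addition reads "amylase, lipase, and thyroid function tests (fT4, and TSH) and LDH".

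On late toxicity, section 11.5 states that immune-related events "may occur shortly after the first dose or several months after the last dose of pembrolizumab treatment". Section 11.8 lists, among likely radiation effects, "Decrease in function of the thyroid gland (if thyroid is in the ISRT field". For both thyroid rows, Table 6 gives the monitoring instruction "Monitor for signs and symptoms of thyroid disorders" and names no laboratory schedule.

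On reporting, section 11.3 states: "AEs should be reported from the time the subject signs consent through 30 days post-last study intervention". After that, the investigator should report events "believed to have a reasonable possibility of being associated with study intervention".

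**The concern.** The protocol names a thyroid effect that can be immune-related, radiation-related or both, and says immune-related events can start well after dosing stops. Its laboratory schedule drops the one test pair that would show such an effect before symptoms, just when the late period begins.

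Safety of front-line pembrolizumab is a secondary objective (section 2.0), analysed in section 14.0 by descriptive tabulation of treatment-related adverse events. Section 11.1 counts an unfavourable laboratory finding as an adverse event, so a laboratory-only thyroid change belongs in those tables if it is detected and attributed to treatment. Without a scheduled test, detection depends on a physician ordering one. For the patient the cost is possible delay in finding a treatable condition. For the report it is possible under-counting of late thyroid events.

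**Working it through.** The plan gives no figure to reproduce. The check compares its sections; the only arithmetic concerns cost.

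**1. Does comp include thyroid tests?** No. In both versions of footnote 6 the analytes of the metabolic panel stand in brackets, and fT4 and TSH stand outside them. The screening windows confirm the separation: 14 days before treatment for comp, 7 days for the thyroid tests.

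**2. What does the grid require at Follow-up?** The combined Hematology and Chemistry row is marked at both End of Treatment and Follow-up. Footnotes 18 and 17 are attached to the Follow-up column header and say which of those tests apply at that visit. The restriction to CBC and comp therefore governs, and the last scheduled TSH/fT4 is at End of Treatment.

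**3. Is a thyroid test scheduled elsewhere?** No.
- Section 10.3 covers EBV PCR and cell-free DNA.
- Table 6 asks for signs and symptoms.
- Section 11.8 lists radiation effects and sets no tests.
- Section 13.0 sets the length of follow-up: to progression, or 2 years after treatment.

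Scheduled TSH/fT4 pairs after End of Treatment are thus zero in either calendar.

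**4. What else could detect a late thyroid event?** Physical examination, vital signs and performance status are marked at Follow-up and could prompt a test in a symptomatic patient. The late rule in 11.3, and the late serious-event rule in 17.2, govern reporting of events already noticed. None of these generates a TSH or fT4 result in a patient without symptoms. That subgroup is the whole of the gap.

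**5. How many patients or events?** The ceiling is the planned enrolment of 19, and fewer in practice because follow-up stops at progression. The documents give neither a thyroid event rate nor the share of patients with the gland in the radiation field, so the number of missed events cannot be estimated.

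**6. What would testing cost?** The Follow-up visit interval is not stated separately. Two intervals in the same footnotes bracket it: EBV PCR every 3 months and imaging every 6 months.
- 3-monthly visits: 12 / 3 = 4 visits in 12 months; 4 x 19 = 76 test pairs.
- 6-monthly visits: 12 / 6 = 2 visits in 12 months; 2 x 19 = 38 test pairs.

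Both are upper bounds, since they assume that all 19 patients stay in follow-up for 12 months.

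**7. How would a result reach the safety data?** Even at 3-monthly visits with the one-month window, the first falls at about 3 - 1 = 2 months, beyond the 30-day routine window. Abnormal results would therefore enter through the late rule in 11.3.

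**The case against.** The strongest reply is that this is a deliberate and reasonable reduction. The word only shows intent. The comp panel retained at Follow-up still covers liver enzymes, bilirubin, creatinine and glucose, so laboratory screening continues for several other toxicities in Table 6. The statement about late onset concerns immune-related events in general, not thyroid events in particular, and the radiation effect is conditional on field. No dosing decision remains after treatment, and even during treatment Table 6 continues pembrolizumab for grade 2 to 4 hypothyroidism. Clinic visits continue and late related events are reportable.

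Most of this stands. It shows that the restriction is a choice, that its consequence is small and that efficacy is untouched. It does not show how an asymptomatic thyroid change after treatment would be found, and the protocol gives no reason for omitting a test of a toxicity it names.

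Two stronger readings are tempting, and the documents do not support them.
- A reader might infer that the calendar contradicts itself, because Chemistry is marked at Follow-up and footnote 6 includes thyroid tests. But the row is combined, so a mark is needed for any blood test at that visit, and the column footnote then narrows it. The calendars do the same elsewhere: footnote 9 limits EBV PCR to odd cycles from cycle 5, and footnote 20 in 10.2 limits PET/CT to the last SMILE cycle.
- A reader might infer that the enrolling sites will test differently. Nothing shows this: the visit-specific instruction is the same for all, and section 16.0 places coordination in one office.

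**Conclusion.** The point holds in a narrow form. After End of Treatment no TSH or fT4 is scheduled in either calendar, so asymptomatic thyroid dysfunction arising then may be found late and under-counted in the descriptive safety tables. Symptomatic cases can still be tested and reported.

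The conclusion rests on reading comp as footnote 6 does and on letting the visit-specific footnote govern. Both follow from the text. That events would in fact be missed is a possibility, not a demonstrated loss. The complete response endpoint, the sample size and dosing decisions do not change. The change is worth making because it is cheap and serves patient safety as well as a secondary objective, but its priority is low.

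**What to change.** In footnote 18 of section 10.1 and footnote 17 of section 10.2, change the permitted Follow-up laboratory tests to CBC, comp, TSH and fT4 only, for example for the first 12 months after the last study treatment. Twelve months is a suggestion; the protocol itself speaks only of several months. State in the same footnotes that abnormal thyroid results considered possibly related to study treatment are recorded under the existing late-event rule in 11.3. The edit also brings the Follow-up footnotes into line with the thyroid part of footnote 6.

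The tests use blood already drawn at existing visits, within the bounds worked out above (76 or 38 pairs). No new visit, procedure or grid mark is needed, and the 30-day window stays as it is. The downsides are some time to assess abnormal results and a possibly higher reported thyroid event count.

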# 10.2 Evaluations during treatment for stage III, IV patients:

Assessment Period	Screening 	Сус	le 1	Су	cle 2	Cycle 3	Су	cle 4		SMILE	Cycles 5	- Cycle 16	Post-Trea	atment
Study Days	Day -28 to 1	Day 1	Day 8-20	Day 1	Day 14-21	Day 1	Day 1	Day 14-21		Post- Cycle 1-3	Day 1	Day 14-21	End of Treatment	Follow up 
Visit Window 	-28 days	- 3 days		+/- 3 days		+/- 3 days	+/- 3 days	+/- 3 days	SMIL		+/- 3 days			+/- 1 month
Informed consent	Х								E					
Medical History	Х								, C					
Review of concomitant medications		Х		х		Х	Х		Cycles	Х	Х		Х	
Review of adverse events		Х		Х		Х	Х		-	Х	Х		Х	
Physical Examination 		Х		Х		Х	Х		3;	Х	Х		Х	Х
Vital Signs 		Х		Х		Х	Х		ISRT		Х		Х	Х
ECOG/KPS		Х		Х		Х	Х		Tif	Х	Х		Х	Х
Hematology  and Chemistry 		Х		Х		Х	Х				Х		Х	Х
HIV, Hepatitis B and Hepatitis C 	Х								indicated					
Pregnancy test 		Х							s] k					
EBV PCR 9		Х		Х			Х		ee		Х		Х	Х
Referral to Radiation Oncology	Х								footnote					
FDG-PET/CT simulation 	Х								not					
MRI nasal cavity (only for patients with nasal cavity disease)	х								e 16]					
ECHO	Х													
ECG	Х													
Pulmonary function tests 11	Х													

Baseline Biopsy or archive tissue 12	Х												
Research Tumor Biopsy 13			Х					Х					
PET/CT	X 				Х			Х	X 		Cycle 8  Cycle 12  Cycle 16 	Х	х
Tumor assessment 14					Х			Х			Cycle 8  Cycle 12  Cycle 16 		
cfDNA 		Х					Х			X 		Х	Х
Pembrolizumab 		Х		Х		Х	Х			Х			

- 1. Each cycle is 21 days in length.
- 2. **Screening assessments** must be completed prior to initiation of treatment. HIV, Hep B and C tests must be done within 6 months of start of treatment. Baseline biopsy must be done prior to treatment. All other assessments must be done within 28 days of treatment, except for laboratory tests which must be done within 14 days of treatment. Pregnancy test is required for females of child-bearing potential and must be done within 7 days of initiating treatment.
- 3. Physical Examination must include height and weight. The patient's weight in kilograms must be determined before the start of each cycle.
- 4. **Vital signs** include: pulse, blood pressure, temperature, respiratory rate, and oxygen saturation.
- 5. **Hematology** must include CBC with differential. Screening CBC done within 14 days of start of treatment. Must be repeated within 3 days of C1D1.
- 6. **Chemistry** must include comprehensive metabolic panel (albumin, alkaline phosphatase, total bilirubin, bicarbonate, BUN, calcium, chloride, creatinine, glucose, potassium, total protein, SGOT [AST], SGPT [ALT], sodium, magnesium, phosphorus), amylase, lipase, and thyroid function tests (fT4, and TSH) and LDH. Screening comp done within 14 days of start of treatment. Must be repeated within 3 days of C1D1. Screening amylase, lipase, thyroid function tests (fT4 and TSH) and LDH must be done within 7 days of start of treatment.
- 7. **HIV, Hep B and Hep C tests** include: HIV I/II antibodies, Hepatitis B surface antigen, core antibody and Hepatitis C antibody. Must be done within 6 months of initiating treatment.
- 8. **Pregnancy test** includes: serum β-HCG or urine pregnancy test for women of child-bearing potential. If the urine test is positive or cannot be confirmed as negative, a serum pregnancy test will be required. Screening pregnancy tests must be performed within 7 days of starting treatment.
- 9. **EBV PCR:** screening EBV PCR must be done within 7 days of start of treatment. It is done on Cycle 2 Day 1, Cycle 4 Day 1, then odd cycles only starting in Cycle 5.
- 10. **Baseline FDG-PET/CT** simulation will be done following an initial consultation in Radiation Oncology and prior to starting therapy. Only required for patients who will be receiving radiation therapy.
- 11. **Pulmonary Function tests** include: DLCO at minimum
- 12. **Baseline tumor biopsy:** all study participants will be required to have a biopsy that confirms extranodal NK/T cell lymphoma. If a biopsy is already done, 20 unstained slides from archived tissue will be requested for correlative studies if possible. The biopsy must be done prior to initiation of treatment.
- 13. **Research biopsies:** on-treatment biopsies are mandatory for all study participants. Biopsies will be done Cycle 1 (between days 8-20), and Cycle 4 (between days 8-20), except in cases where due to the location of disease, biopsy would be associated with unnecessary risk to the patient.
- 14. **Tumor Assessment:** is the response assessment after PET scans. Refer to Section 12.0 Criteria for Therapeutic Response/Outcome Assessment.

- 15. **Pembrolizumab**: Pembrolizumab is administered every 3 weeks (21 days) on Day 1 of each cycle, ± 3 days. Pembrolizumab is given 200m via IVPB infusion over 30 minutes (+/- 5 minutes).
- 16. **Reassessment by PET after 4 Cycles of pembrolizumab**: If Partial Metabolic Response (PMR) by PET, patients may begin 45 Gy of involved site radiation (ISRT) if indicated, and an additional 6 months (8 cycles) of maintenance pembrolizumab. ISRT will begin 2-6 weeks after Cycle 4 of pembrolizumab. Patients with less than PMR will undergo a biopsy. If biopsy shows no evidence of lymphoma, patients will proceed with same treatment as those with PET CR. Patients with less than PMR by PET and persistent evidence of disease on biopsy after 4 cycles of pembro will be taken off study.
- 17. **Follow-up** includes: standard clinic visit and laboratory tests (CBC, comp only). EBV PCR every 3 months for 3 years. Imaging to be obtained every 6 months for 2 years post treatment. cfDNA to be collected 6 months, 1 year, and 2 years into follow up or until a new therapy is initiated.
- 18. PET/CT to be completed at baseline only if the patient will not be receiving radiation therapy.
- 19. Patients will be followed by PET/CT (skull apex to midthigh) If PET/CT is not feasible, patients may be followed with CT CAP plus CT nasal cavity (for patients with nasal cavity disease) after discussion with MSK PI. If followed by PET/CT, additional diagnostic CT is NOT required.
- 20. PET/CT to be done after last cycle of SMILE only may be done prior to treatment on C5D1. All other assessments marked should be done for every cycle of SMILE.
- 21. cfDNA to be collected at C1D1, C4D1, C5D1 of pembrolizumab, end of treatment, and 6 months, 1 year, and 2 years into follow up or until a new therapy is initiated.

